## II. BACKGROUND AND SIGNIFICANCE

---

### Background

Over the last several years, the United States has witnessed enormous changes concerning the public acceptance of marijuana. As of July of 2014, 23 states and the District of Columbia have legalized the medical use of marijuana. In addition, Colorado and Washington have now legalized recreational use of marijuana.

Since the original grant was submitted, Oregon, Alaska, and D.C. have also legalized recreational use. Several other states (e.g., CA, AZ, NV, VT, NH, ME) are likely to follow in 2016. In the first four months of 2014 in Colorado, sales of recreational marijuana totaled approximately \$70,000,000, while sales of medical marijuana were close to \$133,000,000. In addition, officials with the State of Colorado estimate the demand for legal marijuana will exceed 130 metric tons in 2015. This estimate does not include consumption in the black market. Considering how much has already changed on the cultural, political and legal front regarding marijuana use and given how rapidly these changes have taken place, the scientific literature that **should** inform public policy and consumer decisions, especially with respect to harm reduction, is inadequate and outdated.

There are a number of critical limitations in the extant literature that must be addressed if NIDA scientists are to influence the regulation of marijuana. First and foremost, scientists need to understand the effects of commonly used marijuana strains, **as they are used in every day life**, as opposed to relying solely on testing the effects of government grown, low potency marijuana in controlled laboratory experiments. These studies are devoid of external reliability because commonly available strains of marijuana have 3-5x greater potency as compared to strains used in previous laboratory studies and because commonly used methods of administration are very different than the methods used in laboratory studies. It is entirely possible that laboratory based studies underestimate the effects of more potent strains that are widely available. A second limitation is that scientists have focused on the effects of tetrahydrocannabinol (THC) while mostly ignoring the other major cannabinoids found in marijuana. Scientists need to conceptualize the effects of marijuana as the compound action of a number of different cannabinoids. Many cannabinoids may modulate the effects of others and some cannabinoids are more inherently harmful than others (see Huestis, 2007; see our preliminary studies). For example, THC and cannabidiol (CBD), two of the major cannabinoids in marijuana, have different effects. CBD may mitigate some of the negative effects of THC and even have some beneficial effects. In fact, **one major premise of this application, reviewed in detail below, is that the ratio of CBD to THC may be a primary determinant of many of the effects of marijuana, including some of the harmful effects.** The review below will summarize the extant literature on the effects of marijuana, specifically what is known about the effects of the two major cannabinoids, THC and CBD, before discussing the limitations of the literature and significance of addressing these limitations in the context of the current application.

#### **Acute Effects on Mood, Reward, and Cognition**

Literature on the acute effects of marijuana dates back to the 1970s. One of the primary methods used to understand the harmful effects of marijuana has been standardized smoking of marijuana in a laboratory setting. Measures related to cognition and drug reward are collected before and after administration. With respect to self-report measures, a number of studies have found that marijuana acutely increases positive mood and measures of reward (Heishman et al., 1990; Chait & Zacny, 1992; Chait et al., 1988). These effects also appear to follow a dose dependent function based on the THC content of the marijuana (e.g., Hart et al., 2001). Studies have also compared the effects of smoked marijuana to the effects of THC in pill form, suggesting that both forms produce similar effects on subjective ratings of mood and reward (e.g., Hart et al., 2002; Wachtel et al., 2002). More recent studies have found similar results: that acute marijuana use increases subjective effects such as 'high' and 'liking,' (Cooper & Haney, 2008; Schacht, Selling, & [name], 2009) even when using a "balanced placebo" design (see Metrik et al., 2012). Thus, there is a long history of studies in the literature documenting that acute marijuana use produces changes in measures related to positive mood and reward.

Other studies have focused on the harmful cognitive effects of marijuana. Studies suggest that marijuana produces acute cognitive impairment, especially relating to memory and attention during intoxication (for review see Ranganathan & D'Souza, 2006; Lundqvist, 2005). For example, studies that were published as early as the 1970's suggest that marijuana disrupts immediate and delayed free recall of information (e.g. Abel, 1971; Darley et al., 1974). Recall of words from a list is one of the most common approaches to demonstrating the effect of THC on recall performance (e.g., Heishman et al., 1989). Studies have also suggested that acute

marijuana may interfere with working memory, as evidenced by the effect of marijuana on the digit symbol substitution task (DSST), which some studies suggest may be the working memory measure most sensitive to the acute effects of marijuana (see Wilson et al., 1994). In sum, the literature suggests that acute administration of marijuana impairs the encoding and retrieval of information, albeit to a modest degree. However, it is important to note that one of the limitations of this literature is that most, if not all of these studies, have utilized a laboratory administration of low potency marijuana that may not accurately reflect the effects experienced in the real world.

### **Is Greater THC Potency Associated with Greater Harm?**

Recent reviews have suggested that the greater potency of today's marijuana, compared to earlier decades, may lead to significantly greater levels of intoxication and harm (e.g., Volkow et al., 2014). However, only a few previous studies have actually examined the effect of marijuana potency on smoking topography and subjective and cognitive measures, and these studies are outdated. For example, an early study that compared the different potencies of marijuana (.36%, .73%, 1.45% THC) found that individuals who were given the lower potency marijuana smoked significantly more than individuals who smoked the high potency marijuana, suggesting that individuals may compensate for lower potency by simply smoking more (Cappell & Pliner, 1974). However, overall levels of subjective intoxication were still greater in the high potency group, indicating that individuals may smoke less but still experience greater harm with the higher potency marijuana. A subsequent study found no effect of potency on smoking topography (Perez-Reyes et al., 1982). A study published in the late 1980s used a more sophisticated approach to compare marijuana with three different potencies (0, 1.3%, 2.7% THC). Heishman et al. (1989) suggested that individuals significantly changed their smoking topography when receiving the higher potency marijuana, as evidenced by lower puffs and inhalation volumes. Others have also noted changes in topography, such that individuals who receive higher potency marijuana smoke less, even though there were still dose response effects (Kelly, Foltin, & Fischman, 1993). In sum, a handful of studies prior to 1993 suggest that individuals smoke less when they are smoking a higher potency strain, but may still experience greater intoxication and marijuana effects. As noted by Volkow et al. (2014), this literature is seriously limited by the potency of the marijuana used (usually 0 to 3.5%). The THC potency of marijuana in Colorado often exceeds 18%. Studies are desperately needed to examine these higher potency strains.

### **Does CBD Mitigate the Harmful Effects of THC?**

Clearly, the evidence suggests that acute marijuana use is associated with cognitive impairment, mood alterations, and reward responses. However, almost all of this research was conducted with low potency marijuana provided by the government and almost all of this research was focused on the effect of one particular cannabinoid, namely THC. The effects of other cannabinoids, such as CBD, are important to consider when interpreting the harmful effects of marijuana use, especially given that marijuana includes more than 80 additional cannabinoids (Izzo et al., 2009; Huestis, 2007). Strains commonly available in states like Colorado can differ dramatically on the potency of these cannabinoids. As a concrete example regarding the importance of cannabinoids other than THC, several studies have demonstrated that THC and CBD have very different effects on mood and cognition. As noted previously, results from both imaging and non-imaging studies suggest that THC is associated with memory impairment (for review see Ranganathan & D'Souza, 2006), anxiety/negative mood effects (Vann et al., 2008), and positive mood and reward (Bhattacharyya et al., 2012; Cooper & Haney, 2008). Conversely, analyses suggest that CBD may attenuate the negative effects of THC on mood, reward, and cognition (Englund et al., 2013; Hermann & Schneider, 2012; Fusar-Poli et al., 2010; Demirkca et al., 2011; Schubart et al., 2011; Vann et al., 2008; Bhattacharyya et al., 2012; Bhattacharyya et al., 2010; Morgan, Schafer, Freeman, & Curran, 2010). Most of the work on CBD has involved the administration of THC and CBD in pill form. Much less is known about the combined effects of THC and CBD when using

marijuana in the plant form. Given that oral CBD mitigates some effects of THC, this is a high priority area of research in terms of understanding how to reduce the potentially harmful effects of marijuana.

### **Limitations of the Extant Literature**

There are important limitations to the extant literature that must be addressed given the changing landscape. The most important limitation of studies to date is the exclusive use of government produced, low potency marijuana administered in a tightly controlled laboratory environment, which compromises external validity. In all of the studies that used plant material cited above, the source of that material was the NIDA sponsored farm, which is the only legal source for laboratory administration of marijuana in the United States. Until very recently, this supply was derived from seed stock obtained from marijuana grown in Mexico in the 1960s. In effect, all of the studies published through 2006 used this low potency marijuana, while the potency of CBD in this research marijuana was close to zero. As a concrete example of compromised external validity, when we conducted a study with a controlled administration of marijuana in 2006, we were provided with marijuana with a THC potency of 3% (see Schacht et al., 2009). The participants in this study reported that the quality of the marijuana was poor and reported that they had a difficult time smoking it, which is not surprising given the average quality and potency of marijuana in Colorado in 2006 was considerably greater. Consequently, the external validity of that study was compromised. Currently, the THC potency of recreational marijuana in Colorado can exceed 20%, and the potency of CBD comes close to 20% in some strains. One of the often-cited potential harms of marijuana legalization is the availability of high potency marijuana, which may lead to greater levels of intoxication and greater harmful effects (Volkow et al., 2014). Unfortunately, the data on this issue are very limited, if not non-existent. We know nothing about the effects of high potency marijuana. Clearly, we need to develop a knowledge base regarding the effects of commonly used, high THC strains of marijuana in order to understand the harmful effects.

A related limitation is the exclusive reliance on laboratory administration approaches that do not reflect how marijuana is used outside the laboratory. While laboratory studies that emphasize internal validity certainly play an important role in the scientific literature, it is critical that the knowledge base also includes studies that emphasize external validity. Previous laboratory studies often combined the low potency marijuana cigarette with a controlled puffing procedure (see Heishman et al, 1989; Schacht, Selling, & [name], 2009). While this method helps to control the dose across subjects, it may have little to do with how people actually use marijuana, especially given the huge discrepancy in THC potency between what has been traditionally available from NIDA (e.g., 6%) and what is available in a state like Colorado (e.g., 20+%). Thus, prior studies that have relied on government produced marijuana may be underestimating effects given the lower potency of government marijuana. Alternatively, prior studies may be overestimating the effects given that subjects are often asked to smoke an entire marijuana cigarette in 5 minutes (e.g., Schacht, Selling, & [name], 2009). The fact that we know little about harmful effects of high THC marijuana, as it is commonly used in legal states like Colorado, is the primary justification for Specific Aim 1.

The other important limitation of previous studies on the harmful effects of acute marijuana use is that they often ignore other cannabinoids such as CBD, which may mitigate the effects of THC. In fact, the only studies to date that have examined CBD have used a synthetic, pill version. While these studies show that CBD mitigates the effects of THC, marijuana users do not use synthetic THC or synthetic CBD in pill form. Thus, the field desperately needs data regarding how cannabinoids, particularly CBD, may mitigate or exacerbate the harmful effects of THC in the real world, which is the primary justification for Aim 2.

Finally, CBD is just one of 80+ cannabinoids that may mitigate or exacerbate the harmful effects of marijuana. The genetic and chemical diversity of cultivated marijuana is enormous, and the diversity is readily evident in the dispensaries. An examination of dispensaries across Colorado suggests that there are several hundred distinct strains and the primary cannabinoids (THC, CBD, CBG, CBN, THCV) may vary more than 40 fold across these strains. To get a sense of this diversity, see <http://tgscolorado.com/strains> or

<http://riverrockcolorado.com/mainmenu/flowers/>. Some of these cannabinoids, like CBD, may mitigate the harmful effects of THC. Others may exacerbate the harmful effects. While it is beyond the scope of this application to examine all of these cannabinoids, we have included an exploratory aim and analyses to examine additional cannabinoids and to examine the genetic diversity underlying the chemical diversity.

### **Summary of Significance, Impact, and Innovation**

With respect to public education regarding marijuana more generally, harm reduction efforts to date have focused on the message that all marijuana is harmful. This approach is potentially problematic because of numerous reports in the press (e.g. Sanjay Gupta's 2013 CNN report) that some forms of marijuana are showing efficacy at treating seizures in children and other disease states. It is becoming increasingly clear to the lay public that there are many different forms of marijuana. An evidence-based message clearly describing the potential harms of specific forms or compositions of marijuana would be more likely to have an impact in terms of harm reduction efforts. It is expected that the proposed research will generate information about which strains produce the most harmful effects and which strains produce the least harmful effects. Successful dissemination of this information to the public is likely to inform personal decisions about whether to use marijuana and which type of marijuana to use. It will also inform policy makers who seek to develop new regulations, perhaps mandating specific cannabinoid levels, to reduce the harm of recreational marijuana use.

To be more specific about the significance of this application, the proposed research is designed to address the limitations noted above, and in doing so, is expected to have a significant impact on the knowledge base regarding the acute effects of marijuana, as it is used in the real world, particularly with respect to the effect of different levels of THC. The existing literature that relied heavily on low potency marijuana may have little relevance to the situation we face today. Study 1 is significant because it will provide real world data on the degree to which the THC potency of the marijuana leads to greater harm, which others have noted is of paramount importance (Volkow et al., 2014). Study 1 also has direct translational implications. Data linking higher potency to greater harmful effects could be used to inform the public about which types of marijuana to avoid. This information may also be used to eventually identify THC potency targets for future regulatory efforts. Thus, we expect Study 1 to have an important translational impact in terms of harm reduction efforts.

## **III. PRELIMINARY STUDIES**

---

As noted above, the PI ([name]) has conducted prior research on the acute effects of cannabis (Schacht, Selly, and [name], 2009) as well as research on cannabis withdrawal and cue-elicited craving for cannabis (Haughey et al., 2008; Filbey et al., 2009; 2010) and the association between brain structure and cannabis use (Schacht et al, 2011; Weiland et al., 2015). More broadly, his research focuses on the study of neurocognitive and genetic factors underlying response to interventions to decrease substance-use and related risk behavior, and increase health behaviors. The co-PI ([name]) has also studied the association of cannabis use and risk behavior (Bryan et al., 2012) and has extensive experience in research related to health behaviors and interventions. [name] conducted a five year NIDA funded study (Ito, [name], Bryan et al. 2009) which involved over 1000 personal interviews on detailed cannabis use. Thus, they are uniquely qualified to head this research project.

## **IV. RESEARCH STUDY DESIGN**

---

### **Overview and Design of Study 1 (e.g., Aim 1, Hypotheses 1 and 2).**

Study 1 is designed to test the hypothesis that a high THC strain of marijuana will be associated with greater blood levels of THC and greater harmful effects, as compared to a lower THC strain, when used in a

naturalistic environment. To that end, regular flower marijuana users, who, according to our preliminary data, typically use marijuana with a THC potency of ~18%, will be assigned to use one of three strains with no CBD but with different THC potencies (low, medium, or high: e.g. 6%, 12%, or 18% THC for smoked flower) and regular edible marijuana users who typically purchase 10 mg products will be allowed to use as they normally would (producing naturally occurring low, medium, and high groups: e.g. less than 2.5mg to greater than 10 mg THC n=33 per group) for five days prior to participating in the experimental session. Measures will be collected at Appointment 1: (Baseline/**Session 1**), after 5 days of using the assigned strain, but in a sober condition before use in our mobile laboratory at Appointment 2: (**Session 2**), they will then return to their home to use the assigned strain and return to the mobile laboratory (**Session 3**), and 60 minutes after their last use at home (**Session 4**). Details regarding sample ascertainment, marijuana administration, timing of measures to be collected, power analyses, and the analytic plan for Study 1 follow. Thus, Study 1 will involve a 3 Cannabis strains: high, medium, and low THC x 4 (Time: 1, 2, 3, 4) mixed factorial design.

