### **Marijuana Administration at Home.**

Unlike other studies done in the United States to date, the proposed work will utilize a design that is observational but contains some experimental elements. Specifically, at the end of Appointment 1 (Baseline/Session 1) participants will be given instructions to purchase 3 grams of either a normally high THC strain, a medium THC strain, or a low THC strain at a dispensary (The Farm) in Boulder, Colorado. The normally high THC smoked flower strain contains 18% THC and 0% CBD and edibles can range from a low of 2.5 mg to greater than 10 mg of THC and 0 mg of CBD. **Please note the term “high” is relative given that the average potency in Colorado exceeds 18% and edibles are normally packaged in 10 mg THC doses.** The medium flower strain contains 12% THC and 0% CBD. The low flower THC strain contains 6% THC and 0% CBD. Colorado requires all strains of flower and edibles to be tested by a state licensed lab, which allows us to have a precise measure of potency to operationalize our high, medium, and low THC strains. Furthermore, the dispensary that we will work with (The Farm - see letter of support) performs cannabinoid and terpene potency testing on each batch produced. The dispensary will set aside a specific lot of the strains which will be labeled as “Strain A”, “Strain B”, and “Strain C” such that participants, dispensary staff, and research staff will be blind to which strain was purchased. Thus, 3 grams of each marijuana strain will be packaged in childproof bottles labeled as “Strain A”, “Strain B”, and “Strain C.” Our preliminary data suggests that 3 grams is sufficient for the study. [name] (co-investigator) will maintain the blind. The instruction to purchase “A” or

“B” or “C” will be urn randomized across participants such that equal numbers of male and female participants are included in the high, medium, and low conditions. The observational aspect of the design involves the instruction that participants can use as little or as much of the marijuana as they wish during the five days prior to the experimental appointment. The five-day period allows each participant to become accustomed to the strain. Subjects are prompted by email or text message to report how much was used each day using an online reporting system. On the fifth day, the research assistant calls the participant one hour prior to their appointment to remind the participant about the upcoming appointment from the research team.

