### **Power Analysis and Sample Size Requirement for Hypotheses 1 and 2**

Sample size was selected to permit analysis of the primary research questions at two-tailed alpha of .05 and power level of .80. Estimates of effect size follow Cohen (1988) and were conducted in G\*Power 3 (Faul et al., 2007). The primary analysis is the test of the strain X time interaction effects across repeated assessments of THC in the blood as well as assessments of working memory and the rewarding effects of the marijuana. To be conservative, we thus estimated an ICC of .60. Using a mixed model ANOVA design, with three groups, four assessment points, and an average ICC = .6 between assessment points, a total n=99 (33 per group) will allow us to detect an interaction effect as small as  $f=.12$ .

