### **The impact of attrition.**

It is anticipated that some attrition will occur in this population. Based on our current pilot study and previous marijuana studies, we anticipate a 10% attrition rate between Appointment 1 baseline session and Appointment 2 the experimental session, though we have not experienced and do not anticipate differential attrition by condition. Thus, to allow for attrition, we assume a 90% retention rate over the course of data collection. To adjust for this attrition rate, we will recruit  $n\approx 111$  participants ( $n=37$  per group). Our approach to power analysis and accounting for attrition is extremely conservative, in that the techniques we will utilize in data analysis use state of the art recommendations in iterating the estimation of missing data (Schafer & Graham, 2002; Little, 1988). All analyses are intent-to-treat and all available data are utilized in analyses.

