**Hypothesis 2** tests whether blood levels of THC are positively associated with diminished working memory and greater rewarding effects of the marijuana, operationalized with the DEQ. If analyses of Hypothesis 1 show that there are main effects by group suggesting that the higher THC strain results in significantly higher THC levels in the blood than the medium or low THC strains, the between-groups variable for models testing Hypothesis 2 will be group and we will include all four time points. Since participants were randomly assigned to group, this test allows for the highest internal validity in terms of causal conclusions about the effects of THC. If, on the other hand, participants titrate their own use such that there are few reliable between-groups differences, then actual blood levels of THC will become the between-groups (continuous) independent variable in tests of Hypothesis 2 and we will utilize timepoints 3-4 as the within-subjects effect of time. Our preliminary studies confirm wide variability in THC levels even among individuals using the same strain, so there will be adequate between-participant variability for these analyses. In either case, we will again use the RCR approach described above, and standard approaches to the estimation of interactions in regression (Aiken & West, 1991) in the case of a continuous IV (i.e., mean-centering prior to creation of the interaction term). In each model, the predictors will include the group variable (or continuous THC blood levels), a time variable, and their interaction.

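### Edible users are not assigned a THC level, yet the plan gives one group factor, one causal claim based on randomisation and one sample size, none of them split by product

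*Protocol*

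**What the plan says.** The Overview and Design of Study 1 describes two ways into a potency group. Flower users "will be assigned to use one of three strains with no CBD but with different THC potencies". For edible users it says that "regular edible marijuana users who typically purchase 10 mg products will be allowed to use as they normally would", and that this use forms the low, medium and high edible groups. The same section then defines the study as three strains by four times.

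Marijuana Administration at Home says that "participants will be given instructions to purchase 3 grams of either a normally high THC strain, a medium THC strain" or a low one. It urn-randomises the coded purchase across participants and names no exception, although edibles are discussed in the same paragraph. The Appointment 1 procedure in section XII repeats the 3-gram instruction, again without an exception.

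The analysis section for Hypotheses 1 and 2 has one between-subjects factor, strain, at three levels. For Hypothesis 2 the listed predictors are group (or blood THC), time and their interaction. Where group is used, the justification is: "Since participants were randomly assigned to group, this test allows for the highest internal validity in terms of causal conclusions".

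The power section says that "a total n=99 (33 per group) will allow us to detect an interaction effect as small as" f = .12. In the Overview, 33 per group stands inside the parenthesis about edibles. No section says how many of the 99, or of the roughly 111 recruited, are flower users.

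**The concern.** Random assignment supports a causal reading only for people who were assigned. On the Overview's account, an edible user is in the low or high group because of personal habit. That habit may go with tolerance and usual consumption, which bear on all three outcomes: blood THC, working memory and drug reward. Low also means different things for the two products: a percentage of THC in flower, and milligrams in an edible.

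Aim 1 covers both products under the same three labels, and the models contain nothing to keep them apart. Followed as written, the plan could report a partly self-selected difference as a randomised effect of THC potency. The protocol wants its results to inform public advice and potency regulation, so this matters.

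The sample size raises a linked question. The power statement describes the randomised comparison only if all 99 completers are flower users.

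**Working it through.** **1. The sections side by side**

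| Section | Flower users | Edible users |
|---|---|---|
| Overview and Design | assigned to one of three strains | use as usual; groups form by themselves |
| Administration at Home; Appointment 1 | buy a coded 3 g strain | no exception stated |
| Hypotheses 1 and 2 models | one three-level factor | no separate term or model |
| Causal justification | random assignment | no exception stated |

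There are two readings. If the purchase instruction covers everyone, it contradicts the Overview. If it covers flower only, the Overview stands and the randomisation sentence is too broad for any model that includes edible users.

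**2. What a pooled contrast would estimate**

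Let p be the flower share, taken as equal in all groups. Without a product term, the high-minus-low difference is

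p × (flower effect) + (1 − p) × (edible effect + confounding from self-selection).

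Only the first part is protected by randomisation. If p differs between groups, the average difference between flower and edible users is added as well. The protocol gives neither p nor the confounding, so this bias has no number.

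**3. The plan's own sample size**

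Inputs from the power section: "two-tailed alpha of .05 and power level of .80"; "with three groups, four assessment points, and an average ICC = .6 between assessment points"; f = .12; N = 99. For the group-by-time interaction in a repeated-measures ANOVA, with sphericity assumed:

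- λ = f² × N × m / (1 − ρ) = 0.0144 × 99 × 4 / 0.4 = 14.26
- df1 = (3 − 1)(4 − 1) = 6; df2 = (99 − 3)(4 − 1) = 288
- Power from the noncentral F distribution = .811; smallest f detectable at 80% power = .119

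With equal groups, 99 is the smallest total that reaches 80%. For attrition, the plan says "we anticipate a 10% attrition rate between Appointment 1 baseline session and Appointment 2 the experimental session": 33 / 0.9 = 36.7, rounded up to 37 per group, and 3 × 37 = 111. Both stated figures reproduce.

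**4. Power among flower users alone, if the 99 are shared**

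The formula is the same. The flower numbers are assumptions, because the protocol gives no split.

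| Flower completers (assumed) | λ at f = .12 | df2 | Power | Detectable f at 80% |
|---|---|---|---|---|
| 99 | 14.26 | 288 | .81 | .119 |
| 75 | 10.80 | 216 | .67 | .137 |
| 66 | 9.50 | 189 | .60 | .146 |
| 50 | 7.20 | 141 | .46 | .169 |
| 33 | 4.75 | 90 | .30 | .210 |

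If 33 per group is instead meant for each product, completers number 2 × 99 = 198 and recruits 2 × 111 = 222, against the stated 111.

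**The case against.** No sentence says that flower and edible users enter one model. Hypothesis 1 speaks of people who receive a strain, and the Overview assigns strains only to flower users. The models and the randomisation sentence can therefore be read as describing flower users alone. On that reading the causal sentence is true and only the edible analysis is undescribed. A statistical analysis plan, not seen here, could supply it. The protocol also calls its design observational with experimental features, and it relies on blood THC because use is uncontrolled.

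Much of this stands. Pooling is an inference from the single factor, the absent product term and Aim 1's shared labels. The causal sentence is also conditional: group is the predictor for Hypothesis 2 only if Hypothesis 1 shows group differences in blood THC. Otherwise blood THC at times 3 and 4 takes its place and randomisation is not invoked. A reader might infer that the intent-to-treat inference does not exist at all. The documents do not support that, since flower users can be compared by assigned strain.

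A reader might also infer that three edible groups of 33 are implausible because these users typically buy 10 mg products. That does not follow: the product bought is not the amount consumed, and edible users may use as they normally would.

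The objection does not remove the conflict over allocation or the missing split. The observational label does not help either: the section that uses it explains the observational part as freedom over the amount used, not over potency.

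**Conclusion.** The point holds in conditional form. The protocol is inconsistent on how edible users reach their groups, and it makes a randomisation-based claim without excepting them. If they are self-selected and enter the group factor, the claim is unsupported for them and the pooled effect is part randomised, part confounded. The size of that bias cannot be given from the documents.

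The sample-size calculation is correct for 99 people in one randomised comparison. Whether it applies to the flower users is unknown. It does if all 99 are flower users and edible users come on top. If the 99 are shared, flower-only power at f = .12 runs from .67 with 75 flower users to .30 with 33. A reader might take one of these values as the trial's true power. The documents do not support that: the splits are assumed, and the lower values apply only when the 99 are shared and flower users are analysed alone. All values also assume sphericity and the plan's correlation of .6.

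**What to change.** 1. Reconcile the Overview, Marijuana Administration at Home, the Appointment 1 procedure and the Hypothesis 2 text on how edible users are allocated and what they are told to buy.
2. If edible users are self-selected, define the randomised analysis set as flower users and limit the random-assignment and causal wording to that set.
3. Analyse edible users separately as an observational cohort, adjusted for baseline use and, where collected, the baseline outcome. The Timeline Follow-Back already records use over the 30 days before baseline. Blood THC and the cognitive battery are measured at Session 1; the Drug Effects Questionnaire is scheduled only at Sessions 3 and 4, so it has no baseline value. At the least, stratify by product form and make no causal claim for edibles.
4. State how many of the 99 completers and 111 recruits are flower users, say whether the edible groups are inside or on top of these totals, and restate the detectable f for the flower number.

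The cost is wording and possibly a less favourable stated effect, for example .146 instead of .12 if 66 of the 99 are flower users. These changes need no extra participants. Keeping 80% power at f = .12 among flower users would need more of them if the 99 turn out to be shared.
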